#### **BOR Based on Confirmed Responses:**

- Complete Response (CR) = at least two determinations of CR at least 4 weeks apart (with no PD in between)
- Partial Response (PR) = at least two determinations of PR or better (PR followed by PR or PR followed by CR) at least 4 weeks apart (and not qualifying for a CR), with no PD in between
- Stable Disease (SD) = at least one SD assessment (or better)  $\geq$  6 weeks after start date (and not qualifying for CR or PR).
- Non-CR/non-PD (applicable only to participants with non-measurable disease at baseline) = at least one non-CR/non-PD assessment (or better)  $\geq$  6 weeks after start date (and not qualifying for CR or PR).
- Progressive Disease (PD) = PD  $\leq$  12 weeks after start date of study treatment (and not qualifying for CR, PR, non-CR/non-PD or SD).
- Not Evaluable (NE): all other cases.

Confirmation of response is not necessarily required at the next scan, but could be at any subsequent scan before PD. For instance, if a participant has PR-SD-PR or PR-NE-PR at consecutive tumor assessments, the best overall response will qualify for PR.

SD can follow PR only in the rare case that tumor increases by less than 20% from the nadir, but enough that a previously documented 30% decrease from baseline no longer holds. If this occurs the sequence PR-SD-PR is considered a confirmed PR. A sequence of PR – SD – SD – PD would be a best response of SD if the minimum duration for SD definition has been met.

**Confirmed Objective Response (OR)** is defined as a confirmed best overall response of complete response (CR) or partial response (PR) according to RECIST v1.1.

Participants who do not have an on-treatment radiographic tumor assessment due to early progression, who receive anti-tumor treatments other than the study intervention prior to reaching confirmed CR or PR, or who die, progress, or drop out for any reason prior to reaching confirmed CR or PR will be counted as non-responders in the assessment of OR. Each participant will have an objective response status (0: 'no OR'; 1: 'OR').

OR rate (ORR) is the proportion of participants with OR in the analysis set. No formal statistical hypotheses will be tested.

The number and percentage of participants with unconfirmed and confirmed BOR of CR, PR, SD, on-CR/non-PD, PD, and NE will be tabulated.

The unconfirmed and confirmed ORR by dose level will be presented along with the two-sided 95% CI using the Clopper-Pearson method (1934) (exact CI for a binomial proportion as computed by default by the SAS FREQ procedure using the EXACT option).

A swimmer plot displaying some key radiological milestones will be produced by dose level. For each subject, the time on treatment will be represented. In addition, the following information will be displayed: time to confirmed BOR (CR, PR or SD), time to progression, and status at the end of the follow-up (alive or dead).

**Tumor shrinkage (%)** is defined as the percent change from baseline in target lesions (sum of longest diameter for non-nodal lesions and short axis for nodal lesions as reported in the "Sum of diameters (according to RECIST 1.1)" eCRF page)) per time point. The tumor response will be based on the Investigator assessment. It will be derived as:

$$\left( \frac{\text{Sum of target lesions at Week XX} - \text{sum of target lesions at baseline}}{\text{Sum of target lesions at baseline}} \right) \times 100$$

The maximum tumor shrinkage (%) will be derived across all the post-baseline assessments until documented disease progression, excluding assessments after start of new anticancer therapy, as:

$$\text{Minimum} \left( \left( \frac{\text{Sum of target lesions at Week XX} - \text{sum of target lesions at baseline}}{\text{Sum of target lesions at baseline}} \right) \times 100 \right)$$

The tumor shrinkage as well as the first occurrence of a new lesion and participant off study intervention will be displayed against time point (months) in a line plot (spider plot).

In addition, the percent change from baseline in target lesions per time point as well as other relevant information will be presented in a data listing.

A waterfall plot of maximum tumor shrinkage will be created including all participants with measurable disease at baseline and at least one valid post-baseline assessment. The confirmed BOR will also be presented as an annotation on each vertical bar.

In addition, Subject data listings of tumor assessments and responses will be provided, including lesion number, description and location, type of lesion, imaging date, assessment method, diameter (mm), sum of diameter of target lesions (mm), confirmed BOR and best percent change in sum of

diameters (as recorded from the “Target Lesions”, “Sum of Diameters”, “Non-Target Lesions”, “New Lesions” and “Assessment of disease based on imaging” eCRF pages).

#### 14.2.2 Secondary Endpoint: Progression Free Survival (PFS)

**Progression Free Survival (PFS)** time is defined as the time (months) from start date to the date of the first documentation of objective PD or death due to any cause, whichever occurs first. The tumor response will be determined according to RECIST 1.1 and assessed by Investigator.

$$\text{PFS time (in months)} = (\text{Date of PD or death} - \text{start date} + 1) / 30.4375 \text{ (months)}$$

PFS data will be censored on the date of the last adequate tumor assessment for participants who do not have an event (PD or death), or with an event after two or more missing tumor assessments. Participants who do not have a baseline tumor assessment or who do not have any post-baseline tumor assessments will be censored on the start date unless death occurred on or before the time of the second planned tumor assessment in which case the death will be considered an event.

The last adequate tumor assessment is defined as the last tumor assessment result that is not “NE” or “NA”.

The censoring and event date options to be considered for the PFS analysis is presented in Table 5.

**Table 5 Progression-free Survival Event / Censoring**

PFS Event Status		Censoring	Date of event / censoring
Progressed or died	Before any planned tumor assessment or within two subsequent scheduled tumor assessments after last response assessment of CR, PR or SD	Event	Minimum (Date of PD, Date of death)
	Otherwise	Censored	Date of last tumor assessment with outcome CR, PR or SD or date of first dose of study intervention, whatever is later
Neither progressed nor died		Censored	Date of last tumor assessment with outcome CR, PR or SD or date of first dose of study intervention, whatever is later

Kaplan-Meier estimates (product-limit estimates) will be presented together with a summary of associated statistics including the median PFS time with two-sided 95% CIs. In particular, the PFS rate at 3, 6 and 12 months and estimates for every 6 months will be estimated with corresponding two-sided 95% CIs. The CIs for the median will be calculated according to Brookmeyer and Crowley and the CIs for the survival function estimates at the time points defined above will be derived using the log-log transformation according to Kalbfleisch and Prentice (conftype=loglog default option in SAS Proc LIFETEST) with back transformation to a CI on the

untransformed scale. The estimate of the standard error will be computed using Greenwood's formula.

The PFS time or censoring time and the reasons for censoring will also be presented in a participant listing.

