1.3.1 Part 1A – M4076 Monotherapy Dose Escalation (Daily Dosing)

The schedule of events for Part 1A are provided in [Table 1](#).

The Part 1A fasting window is defined as: 2 hours predose to 1-hour postdose in general, and ~~C~~ hours predose to 4 hours postdose on days where PK-time matched triplicate ECGs are collected.

~~C~~
I

Table 1 Schedule of Activities: M4076 Monotherapy Dose Escalation (Daily Dosing), Part 1A

Assessments and Procedures	Screen (D -28 to -1)	DLT Period (21 days)					Subsequent 3-week Periods (21 days)			End of Study Intervention Visit	Safety Follow up/ Discontinuation Visit	Notes
Day		1	2	8	9	15	1	8	15	Within 7 days after last dose	30 days after last dose	
Visit Window (days)		-1								+7	+/- 7	Day 1 assessments that could be completed on Day -1 are limited to physical examination, height/weight, and ECOG performance status.
Study Site Visits	X	X	X	X	X	X	X	X	X	X	X	Starting Cycle 4, visits at Day 8 and Day 15 are optional
Written informed consent	X											
Inclusion / Exclusion Criteria	X											
Medical History (includes substance usage); Demography	X											Substances: tobacco use only.
Hepatitis B and C tests	X											To rule out active infection, performed at the Investigator's discretion. See Appendix 6 for details.
Optional HIV Screening	X											HIV testing is optional at the Investigator's discretion unless required locally.

Assessments and Procedures	Screen (D -28 to -1)	DLT Period (21 days)					Subsequent 3-week Periods (21 days)			End of Study Intervention Visit	Safety Follow up/ Discontinuation Visit	Notes
Day		1	2	8	9	15	1	8	15	Within 7 days after last dose	30 days after last dose	
Visit Window (days)		-1								+7	+/- 7	Day 1 assessments that could be completed on Day -1 are limited to physical examination, height/weight, and ECOG performance status.
Serum Pregnancy Test (WOCBP only)	X									X		See Section 8.3.5.
Urine Pregnancy Test (WOCBP only)		X				X						Urine β -hCG results must be available prior to M4076 dosing.
Physical Examination	X	X		X	X	X				X	X	See Section 8.2.1.
Height and Weight	X	X				X				X	X	Collect height at Screening only.
Imaging Disease Assessment (CT/MRI)	X	X (at the end of every 6 weeks for the first 24 weeks, then every 12 weeks)								X		Tumor assessment according to RECIST 1.1 until disease progression, end of study, or death, whichever is earlier. See Section 8.1 for details of imaging.

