Tumor assessments	
All investigation dates (e.g. X-ray, CT scan) must be completed with day, month and year.
 
If there are multiple scan dates associated with an evaluation, i.e., radiological assessments occur over a series of days rather than the same day, the choice of date of assessment could impact the date of progression and/or date of response. If there are multiple scan dates associated with an evaluation, the earliest of the scan dates associated with the evaluation will be used as the date of assessment.
 
If one or more investigation dates for an evaluation are incomplete but other investigation dates are available, the incomplete date(s) are not considered for calculation of the assessment date and assessment date is calculated as the earliest of all investigation dates (e.g. X-ray, CT-scan).
 
If all measurement dates for an evaluation have no day recorded, the 1st of the month is used.
 
If the month is not completed, for any of the investigations for an evaluation, the respective assessment will be considered to be at the date which is exactly between the previous and the following assessment. If both a previous and following assessments are not available, this assessment will not be used for any calculations.

Dates of subsequent anti-cancer therapy	
Incomplete dates for start date of subsequent anti-cancer therapy (drug therapy, radiation, surgery) will be imputed as follows and will be used for determining censoring dates for efficacy analyses and in the derivation of the end of on-treatment period.
 
If only day is missing, it will be imputed as the last day of the month unless the end date of subsequent anti-cancer therapy is before that date. In that case, the incomplete anti-cancer therapy start date will be imputed as the end date of the anti-cancer therapy.

	If both day and month are missing, no imputation will be performed. Incomplete subsequent anti-cancer therapy stop dates will not be imputed.
--	--

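### SAP Table 5 conflicts with the SAP text and the protocol on PFS when no CR, PR or SD came first: read as written, it censors first-scan progression at first dose

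*SAP*

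**What the plan says.** **SAP 14.2.2, text.** PFS runs from the start date to objective PD or death. An event is censored only when it comes late: "or with an event after two or more missing tumor assessments". Censoring is at the last adequate assessment: "The last adequate tumor assessment is defined as the last tumor assessment result that is not" NE or NA. Participants with no baseline or no post-baseline assessment are censored at the start, with one exception: "unless death occurred on or before the time of the second planned tumor assessment in which case the death will be considered an event". It then adds: "The censoring and event date options to be considered for the PFS analysis is presented in Table 5".

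**SAP Table 5.** PD or death is an event if it falls "Before any planned tumor assessment or within two subsequent scheduled tumor assessments after last response assessment of CR, PR or SD". Any other event, and every participant without an event, is censored at "Date of last tumor assessment with outcome CR, PR or SD or date of first dose of study intervention, whatever is later".

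**Protocol 9.4.1, Table 16.** The DoR censoring rules apply to PFS. An event is censored only after two or more missed scheduled assessments. Participants with no baseline or no post-baseline assessment are censored at the start of study intervention, with no exception for death.

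**Related places.** Protocol Table 1 schedules imaging "at the end of every 6 weeks for the first 24 weeks, then every 12 weeks", so the first two planned scans are at Weeks 6 and 12. SAP 14.2.1 defines non-CR/non-PD as a result for participants with non-measurable disease at baseline. SAP Section 7 declares no changes from the protocol.

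**The concern.** Table 5 does not cover participants who have an event, or a usable scan, with no earlier CR, PR or SD.

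1. **PD at the first planned scan.** It is not before that scan and follows no CR, PR or SD, so the table censors it at first dose. PD at a later scan after only an NE result fails in the same way.
2. **Non-CR/non-PD only.** Table 5 does not list this result. These participants are censored at first dose, all their follow-up is lost, and most later PDs and deaths go uncounted. Such participants can be enrolled, because protocol 5.1 does not require measurable disease.
3. **Death with no post-baseline scan.** The protocol, the SAP text and Table 5 treat it differently, and Section 7 does not say so.

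The SAP gives neither text nor table precedence. At stake is whether the reported Kaplan-Meier PFS rates can be reproduced, and whether documented progressions leave the risk set on Day 1.

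**Working it through.** **Rules side by side.** Planned scans are at Day 42, Day 84 and Day 126 (protocol Table 1). All cases have a baseline scan. E = event, C = censored, with study day.

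| Case | Protocol Table 16 | SAP text | SAP Table 5 |
|---|---|---|---|
| PD at planned Week 6 scan | E42 | E42 | C1 |
| PD on a Day 40 scan, before the planned date | E40 | E40 | E40 |
| NE at Week 6, PD at Week 12 | E84 | E84 | C1 |
| SD at Week 6, PD at Week 12 | E84 | E84 | E84 |
| Non-CR/non-PD at Weeks 6, 12, 18; no event | C126 | C126 | C1 |
| Non-CR/non-PD at Weeks 6, 12; PD at Week 18 | E126 | E126 | C1 |
| Death Day 30, no scan | C1 | E30 | E30 |
| Death Day 60, no scan | C1 | E60 | C1, or E60 |
| Death Day 100, no scan | C1 | C1 | C1, or E100 |

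The second Table 5 entry applies if its opening condition means before any assessment was done, rather than before the first planned date. Neither reading reproduces the SAP text: the first loses the Day 60 death and the second adds the Day 100 death. Neither restores non-CR/non-PD.

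**Illustration of size.** The plan states no PFS rate, so there is no figure to reproduce and every input here is assumed: exponential times, progression and death independent, no missed scans, median progression mP of 8, 12, 16 or 24 weeks, median death mD of 26, 39 or 52 weeks (12 scenarios). Let h(t,m) = 2^(-t/m) and T = 3 × 30.4375/7 = 13.04 weeks. Let e be the share of first-scan PDs found before the planned date, and p the share with non-measurable disease (same prognosis, no CR).

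- SAP text: S = h(12,mP) × h(T,mD)
- First-scan PD: F = (1 − h(6,mP)) × h(6,mD)
- Table 5: (1 − p)S / [1 − F(1 − e) − p × h(6,mP) × h(6,mD)]
- Protocol early-death rule: S / h(6,mD)

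Central case, mP = 12 and mD = 39: S = 0.500 × 0.793 = 39.7%. F = (1 − 0.707) × 0.899 = 0.263. Table 5 with e = 0 and p = 0 gives 0.3965/0.737 = 53.8%. The protocol rule gives 0.3965/0.899 = 44.1%.

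| Assumption | Central 3-month PFS | Difference from SAP text, 12 scenarios (points) |
|---|---|---|
| Table 5, e = 0, p = 0 | 53.8% | +7.8 to +17.8 |
| Table 5, e = 0.5, p = 0 | 45.7% | +3.6 to +6.8 |
| Table 5, e = 0.75, p = 0 | 42.4% | +1.8 to +3.1 |
| Fault 2 alone (e = 1, p = 0.2) | 36.3% | -3.4 to -2.7 |
| Table 5, e = 0, p = 0.2 | 52.0% | +5.5 to +16.4 |
| Table 5, e = 0.5, p = 0.2 | 42.8% | +0.7 to +4.1 |
| Table 5, e = 0.75, p = 0.2 | 39.3% | -1.4 to +0.1 |
| Protocol early-death rule | 44.1% | +2.5 to +8.7 |

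The last row implies that 8% to 15% die by Week 6 (1 − h(6,mD)), which nothing in the documents supports or excludes.

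For one dose level of 6 (the minimum at the MTD or RDE, protocol 4.1.1), suppose 3 have first-scan PD and 3 are event-free past 3 months. The SAP text gives 3/6 = 50%. Table 5 gives 3/3, 3/4, 3/5 or 3/6 (100%, 75%, 60% or 50%) if 0, 1, 2 or 3 of those PDs were scanned early.

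For scale, the log-log 95% CI around 39.7% with 28 participants, the upper planned size of Part 1A, is about 22% to 57%.

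**The case against.** The strongest reply is that nobody would program fault 1 as written. PD needs a scan, since SAP 14.2.1 excludes clinical deterioration as documented progression. Read literally, the table's opening condition could then apply to PD only on early or off-schedule scans. The SAP text and the protocol both count first-scan PD, and 14.2.2 introduces the table only as options. A Day 1 censoring would also show in the listing of censoring reasons and against the swimmer plot, and a data review meeting precedes database lock.

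Much of this stands: fault 1 is probably a drafting slip and might well be caught. It does not settle the matter, because the text names the table as the place for event and censoring dates. Nor does the charitable reading repair non-CR/non-PD or agree with the text on early death.

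Two stronger readings are tempting. A reader might infer that Table 5 inflates PFS by some 14 points. The documents give no progression times, imaging window or share with non-measurable disease, and with three-quarters of first-scan PDs early and 20% non-measurable the net change is about nil. A reader might also join to this the sentence in SAP 9.8 that subsequent-therapy dates "will be used for determining censoring dates for efficacy analyses", for which no PFS rule exists. That looks like leftover wording: the same sentence also feeds those dates into the on-treatment period, which SAP 9.6 does not do, and the modification history records removal of the subsequent-therapy analysis. It is a separate, minor matter.

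**Conclusion.** The conflict holds on the wording alone and needs no assumption. For participants with no earlier CR, PR or SD, Table 5 disagrees with the SAP text and protocol Table 16 on first-scan PD and on non-CR/non-PD results. The early-death rule differs in all three places, so the no-changes statement in SAP Section 7 is wrong on that point.

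The size is not established. Fault 1 raises PFS and fault 2 lowers it, and the figures above only illustrate what assumed inputs would give. They are not an expected bias.

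The consequence is limited. PFS is secondary in an exploratory study without hypothesis tests (protocol 9.1), and the illustrated differences are within sampling error at these sizes. A reader might infer a threat to dose selection, but DLT and MTD conclusions do not use PFS. DoR is restricted to confirmed responders (SAP 14.2.3), so the first-scan and no-scan faults do not arise there. What remains is an avoidable ambiguity in a prespecified output, which should be corrected before the analysis is programmed.

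**What to change.** All changes are to the SAP.

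- **Event rule.** Revise Table 5 to match the text: PD or death, including PD at the first post-baseline scan, is an event unless it follows two or more missed scheduled assessments since the last adequate assessment.
- **Non-CR/non-PD.** Add it to CR, PR and SD wherever Table 5 names the last assessment.
- **No baseline assessment.** Keep the rule, common to the protocol and the SAP text, that these participants are censored at the start date.
- **Early death.** For participants without a baseline or post-baseline assessment, put one rule in its own row, identical in text and table. Either keep the exception in the SAP text and list it in Section 7 as a departure from protocol Table 16, or delete it and follow the protocol. The documents do not dictate which.
- **Separate tidying.** In SAP 9.8, either remove the words on efficacy censoring dates or state the rule they refer to.

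The cost is a revised table, a few sentences and possibly one Section 7 entry. No protocol amendment and no new data are needed.

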### 14.2.3 Secondary Endpoint: Duration of Response (DoR)

DoR is defined, for participants with confirmed objective response only, as the time (months) from first documentation of objective response (CR or PR) to the date of first documentation of PD or death due to any cause. If a participant has not had an event (PD or death), DoR is censored at the date of last adequate tumor assessment. The censoring rules for DoR are as described for PFS (Section 14.2.2).

The last adequate tumor assessment is defined as the last tumor assessment result that is not "NE" or "NA".

$$\text{DoR (months)} = [\text{date of event or censoring} - \text{first date of OR} + 1]/30.4375$$

Kaplan-Meier estimates (product-limit estimates) will be presented together with a summary of associated statistics including the median DoR time with two-sided 95% CIs. In particular, DoR rate at 3, 6, 12 months and estimates for every 6 months thereafter will be estimated with corresponding two-sided 95% CIs. The CIs for the median will be calculated according to Brookmeyer and Crowley (1982) and CIs for the survival function estimates at the time points defined will be derived using the log-log transformation according to Kalbfleisch and Prentice (1980) (conftype=loglog default option in SAS Proc LIFETEST) with back transformation to a CI on the untransformed scale. The estimate of the standard error will be computed using Greenwood's formula.

DoR will be displayed graphically and analyzed using Kaplan-Meier methodology analogous to that used for PFS as described in Section 14.2.2. If the number of participants with OR is small, the Kaplan-Meier method may not provide reliable estimates. In this case, only descriptive statistics or listings will be provided.

## 15 Safety Analyses

This section includes specifications for summarizing safety endpoints that are common across clinical studies such as adverse events, laboratory tests and vital signs.

The DLT analysis will be performed on the DLT analysis set. All other safety analyses will be performed on the SAF analysis set.

### 15.1 Dose Limiting Toxicities (DLT) Analysis

Of note, DLT as per SMC decision will be available in the table “Review of data” in the SMC minutes. In case a new DLT appears after the DLT period, the minutes will be updated.

For primary analysis, a table will display the following (per dose level (and regimen if different regimens are tested)) and in total for Part 1A and Part 1B) for the DLT analysis set:

- Number and percentage of participants with a DLT per investigator’s judgement as recorded in eCRF (using DLT flag from the AE CRF page)
- Number and percentage of participants with a DLT per SMC decision

A listing of DLTs (per investigator and/or per SMC) will be provided by dose level and participant, including whether it was judged to be a DLT by investigator and/or by SMC.

This listing will additionally contain age, sex, site of primary tumor, SOC, PT, verbatim, CTCAE grade, SAE (yes/no), DLT per investigator (yes/no), DLT per SMC, relatedness to M4076 (yes/no), start date (+treatment day), stop date (+treatment day), duration (in days), action taken with M4076, if treatment was stopped before start of AE: days since stop of treatment, and outcome.

In addition, the following will be presented:

- Mean and Quantiles (2.5%, 25%, 50%, 75%, 95% and 97.5%) for the posterior probability of a participant experiencing a DLT at each of the dose levels used in the study according to the same Bayesian Logistic Regression Model (BLRM) as described in the SMC IAP (see Appendix18.2) or SMC charter (if change occurred). For this analysis either SAS or R (using the package bcrm or crmPack) will be used.

